## Definition of an SAE

If an event is not an adverse event according to the above definition, then it cannot be an SAE even if serious conditions are met (e.g., hospitalization for signs/symptoms of the disease under study, death due to progression of disease).

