Study IFX-1-P2.1 (subjects with early septic organ dysfunction): in this Phase II study in subjects with early septic organ dysfunction caused by pulmonary or abdominal infection, the safety, pharmacokinetics, pharmacodynamics, and efficacy of IFX-1 were investigated in 3 different dose groups (IFX-1  $2 \times 2$  mg/kg,  $2 \times 4$  mg/kg, and  $3 \times 4$  mg/kg, each with a placebo control). In total, 48 subjects were treated with IFX-1. IFX-1 was safe and well tolerated. The following adverse events were reported by the investigator as at least possibly related to IFX-1: acute hepatic failure, hepatocellular injury, pulmonary embolism, hypertension, atrial fibrillation, and impaired healing.

*Study IFX-1-P2.2 (subjects undergoing complex cardiac surgery)*: in this Phase II study in subjects undergoing complex cardiac surgery, the efficacy, pharmacokinetics,

InflaRx Clinical Study Protocol, Version 4.0 Including Amendment 02, 14 May 2020 IFX-1 IFX-1-P2.7

pharmacodynamics, and safety of single doses of IFX-1 were investigated in 4 different dose groups (IFX-1 1, 2, 4, and 8 mg/kg, each with a placebo control). In total, 82 subjects were treated with IFX-1. IFX-1 was safe and well tolerated. The following adverse events were reported by the investigator as at least possibly related to IFX-1: leukocytosis, impaired healing, blood pressure decreased, and heart rate decreased.

*Study IFX-1-P2.3 (subjects with moderate to severe hidradenitis suppurativa)*: in this Phase II study in subjects with moderate to severe hidradenitis suppurativa, the safety, pharmacokinetics, pharmacodynamics, and efficacy of IFX-1 were investigated after 9 weekly infusions of 800 mg. In total, 12 subjects were treated with IFX-1. IFX-1 was safe and well tolerated. There were no adverse events reported by the investigator as at least possibly related to IFX-1.

*Study IFX-1-P2.4 (subjects with moderate to severe hidradenitis suppurativa)*: in this Phase II study, 177 subjects were treated with either placebo or one of 4 different dose regimens of IFX-1 (400 or 800 mg every four weeks and 800 or 1200 mg every two weeks). The IFX-1 treatment was well tolerated and although most subjects experienced TEAEs, these were for the most part non-serious and similar in all treatment groups. IFX-1 treatment was associated with low immunogenicity.

Further details on IFX-1 are given in the investigator's brochure (the current version is available in the investigator site file).

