**Events Meeting the Adverse Event Definition** 

- Any abnormal laboratory test results (hematology, clinical chemistry, or urinalysis) or other safety assessments (e.g., ECG, radiological scans, vital signs measurements), including those that worsen from baseline, considered clinically significant in the medical and scientific judgment of the investigator (i.e., not related to progression of underlying disease).
- Exacerbation of a chronic or intermittent pre-existing condition including either an increase in frequency and/or intensity of the condition.
- New conditions detected or diagnosed after IMP administration even though it may have been present before the start of the study.
- Signs, symptoms, or the clinical sequelae of a suspected drug-drug interaction.
- Signs, symptoms, or the clinical sequelae of a suspected overdose of either IMP or a concomitant medication. Overdose per se will not be reported as an adverse event/SAE unless it is an intentional overdose taken with possible suicidal/self-harming intent. Such overdoses should be reported regardless of sequelae.
- "Lack of efficacy" or "failure of expected pharmacological action" per se will not be reported as an adverse event or SAE. Such instances will be captured in the efficacy assessments. However, the signs, symptoms, and/or clinical sequelae resulting from lack of efficacy will be reported as adverse event or SAE if they fulfil the definition of an adverse event or SAE.

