#### Events NOT Meeting the Adverse Event Definition

- Any clinically significant abnormal laboratory findings or other abnormal safety assessments which are associated with the underlying disease, unless judged by the investigator to be more severe than expected for the subject's condition.
- The disease/disorder being studied or expected progression, signs, or symptoms of the disease/disorder being studied, unless more severe than expected for the subject's condition.

InflaRx	Clinical Study Protocol,
	Version 4.0 Including Amendment 02, 14 May 2020
IFX-1	IFX-1-P2.7

- Medical or surgical procedure (e.g., endoscopy, appendectomy): the condition that leads to the procedure is the adverse event.
- Situations in which an untoward medical occurrence did not occur (social and/or convenience admission to a hospital) or planned hospitalizations due to a pre-existing condition that has not worsened (e.g., elective surgery).
- Anticipated day-to-day fluctuations of pre-existing disease(s) or condition(s) present or detected at the start of the study that do not worsen.

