#### An SAE is defined as any untoward medical occurrence that, at any dose:

- Results in death
- Is life-threatening

Life-threatening in the definition of "serious" refers to an event in which the subject was at risk of death at the time of the event. It does not refer to an event which hypothetically might have caused death, if it were more severe.

• Required inpatient hospitalization or prolongation of existing hospitalization

In general, hospitalization signifies that the subject has been detained (usually involving at least an overnight stay) at the hospital or emergency ward for observation and/or treatment that would not have been appropriate in the physician's office or outpatient setting. Complications that occur during hospitalization are adverse events. If a complication prolongs hospitalization or fulfills any other serious criteria, the event is serious. When in doubt as to whether "hospitalization" occurred or was necessary, the adverse event should be considered serious.

Hospitalization for elective treatment of a pre-existing condition that did not worsen from baseline is not considered an adverse event.

• Results in persistent disability or incapacity

The term disability means a substantial disruption of a person's ability to conduct normal life functions. This definition is not intended to include experiences of relatively minor medical significance such as uncomplicated headache, nausea, vomiting, diarrhea, influenza, and accidental trauma (e.g., sprained ankle) which may interfere with or prevent everyday life functions but do not constitute a substantial disruption.

- Is a congenital anomaly or birth defect
- Other situations:
  - Medical or scientific judgment should be exercised in deciding whether SAE reporting is appropriate in other situations such as important medical events that may not be immediately life-threatening or result in death or hospitalization but may jeopardize the subject or may require medical or surgical intervention to

InflaRx Clinical Study Protocol, Version 4.0 Including Amendment 02, 14 May 2020 IFX-1 IFX-1-P2.7

> prevent one of the other outcomes listed in the above definition. These events should usually be considered serious. Examples of such events include invasive or malignant cancers, intensive treatment in an emergency room or at home for allergic bronchospasm, blood dyscrasias or convulsions that do not result in hospitalization, or development of drug dependency or drug abuse.

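### Appendix 3 leaves ulcer worsening judged as expected disease course outside AEs and SAEs, without a criterion for that judgement, so drug-related worsening can go uncounted in the primary safety endpoint

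*Combined protocol and SAP*

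**What the plan says.** The primary endpoint is the occurrence, nature and intensity of TEAEs, related TEAEs, serious TEAEs and adverse events of special interest (Synopsis, Objectives and Endpoints; section 10.3.1). What counts is settled in Appendix 3, where four entries bear on ulcer worsening:

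- Events Meeting the Adverse Event Definition includes "Exacerbation of a chronic or intermittent pre-existing condition including either an increase in frequency and/or intensity of the condition". Pyoderma gangrenosum is not excepted.
- Events NOT Meeting the Adverse Event Definition lists "The disease/disorder being studied or expected progression, signs, or symptoms of the disease/disorder being studied, unless more severe than expected for the subject's condition".
- Definition of an SAE opens with a condition: an event that fails the AE definition cannot be an SAE, "even if serious conditions are met (e.g., hospitalization for signs/symptoms of the disease under study, death due to progression of disease".
- The seriousness list then begins: "An SAE is defined as any untoward medical occurrence that, at any dose". Death and inpatient hospitalization are among its criteria.

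The Assessment of Causality part of Appendix 3 asks for a relatedness judgement on AEs and SAEs. Section 9.4.8.1 sets 24-hour reporting for SAEs. The trial is open-label and not randomized (section 7.1.4), and all subjects receive IFX-1.

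**The concern.** Section 3.3.3 foresees deterioration from the fluctuating course of the disease. With no control arm, an investigator who sees an ulcer worsen has nothing in the trial to separate drug effect from natural course. Appendix 3 nevertheless asks for that separation first. If the worsening is judged expected, it is not an AE. It then needs no relatedness assessment and no SAE report, and it cannot appear in the primary safety tables even if the subject is hospitalized or dies.

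A drug effect on healing cannot be dismissed. Section 3.2.1 lists impaired healing among the events reported as at least possibly related in the sepsis study, and again in the cardiac surgery study: "at least possibly related to IFX-1: leukocytosis, impaired healing, blood pressure decreased, and heart rate decreased". This trial treats open wounds. The sponsor also uses safety data from small numbers to decide whether the next dosing group opens (section 9.4.9).

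**Working it through.** The plan states no figure to reproduce: section 10.1 says that no formal sample size estimation was made. The check is therefore a reading of the rules, followed by simple arithmetic for scale.

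**Step 1. Follow one event through Appendix 3.** Suppose that an ulcer worsens on treatment and the subject is admitted.

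- Under the exacerbation entry, the worsening of a chronic pre-existing condition is an AE. The admission makes it an SAE.
- Under the disease exemption, with the worsening judged expected, it is not an AE. The conditional sentence in Definition of an SAE then keeps it from being an SAE despite the admission.
- Under the disease exemption, with the worsening judged worse than expected, it is an AE and an SAE.

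The same event has two outcomes, depending on which entry is applied and on a judgement for which the protocol gives neither a criterion nor an independent adjudicator.

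**Step 2. Look for a rule that breaks the tie.**

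- Sequelae of lack of efficacy are reportable only if they fulfil the AE or SAE definition, which leads back to the same question.
- The instruction to treat doubtful hospitalizations as serious concerns seriousness, not whether the event is an AE.
- Adverse events of special interest are always reported as SAEs. The list covers infusion-related reactions, meningitis, meningococcal septicemia and invasive infection, but not ulcer worsening.

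None of these closes the gap.

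**Step 3. Follow the consequence.** Relatedness is assessed for AEs and SAEs only. An event classed as expected course drops out before anyone must ask whether IFX-1 caused it. It is therefore missing from TEAEs, related TEAEs and serious TEAEs together.

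**Step 4. Weight of one uncounted subject.** Inputs: 3 groups of 6, so 3 × 6 = 18 (section 7.1.2), and at least 5 patients for an escalation decision (section 9.4.9). The weight is 1/n.

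| n | 1/n |
|---|---|
| 5 | 20.0 points |
| 6 | 16.7 points |
| 18 | 5.6 points |

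Exact 95% limits show the same. With 0 events the upper limit is 1 − 0.025^(1/n), which is 45.9% for n = 6 and 18.5% for n = 18. With 1 event the Clopper-Pearson interval is 0.4% to 64.1% for n = 6 and 0.1% to 27.3% for n = 18.

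**Step 5. How often the rule could come into play.** The documents give no rate of serious ulcer worsening, so the rates p below are assumptions. The chance of at least one such event, from any cause, is 1 − (1 − p)^n.

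| Assumed p | n = 6 | n = 18 |
|---|---|---|
| 5% | 26.5% | 60.3% |
| 10% | 46.9% | 85.0% |
| 20% | 73.8% | 98.2% |

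These are chances that a case arises to be classified. They are not chances that it is wrongly excluded.

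**The case against.** A reader might infer that Appendix 3 bars every hospitalization or death from pyoderma gangrenosum from being an SAE. It does not. The sentence in Definition of an SAE is conditional, and its examples illustrate events that have already failed the AE definition. The exemption reaches only "expected progression, signs, or symptoms of the disease/disorder being studied, unless more severe than expected", so worsening beyond that is an AE, and an SAE if serious. Nor does that sentence flatly contradict the seriousness list. The two can be read in order: first whether the event is an AE, then whether it is serious. The real tension lies between the exacerbation entry and the disease exemption.

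A reader might also apply the 10-20% inpatient death rate from section 3.2.2 to gauge lost SAEs. That does not work. The same paragraph says that deaths may be due to comorbidities, an associated disorder or treatment, and such deaths would not fall under disease progression. The trial also excludes subjects in poor general condition that might affect wound healing.

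The earlier signal is modest. Section 3.2.1 gives no counts and no comparison with the placebo controls of those two studies, and the open-label hidradenitis study reported no related events.

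Worsening is also recorded elsewhere. A Physician's Global Assessment of 6 means worse. That score, ulcer area and ulcer volume are reviewed with adverse events at each interim analysis (section 10.3.6). Section 9.4.9 refers to safety data without limiting it to events classed as AEs. Early discontinuations are documented (section 8), so a death would not vanish from the records.

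Finally, counting every disease admission as an SAE brings background disease into a single-arm safety count.

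Most of this stands and limits the point, but the gap remains. The efficacy endpoints follow the target ulcer, while multiple ulcerations are one of the features that can qualify a subject, so a new or non-target ulcer may be missed. Those measures record neither hospitalization nor causality, and they lie outside the primary endpoint.

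**Conclusion.** The point holds in a limited form. Worsening of pyoderma gangrenosum judged to be expected is outside AEs and SAEs even if it leads to hospitalization or death. The threshold for that judgement is undefined, and another entry in the same appendix points the other way. Drug-caused worsening classed this way would escape causality assessment and the primary safety tables.

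The effect can only lower the reported AE and SAE rates. It is 16.7 percentage points per uncounted subject in a group of 6 and 5.6 points in 18. How many subjects would be affected cannot be derived from the documents.

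The conclusion rests on two assumptions: that some investigators would apply the exemption rather than the exacerbation entry, and that the safety endpoint is meant to describe all serious untoward events on treatment. If only events beyond the natural course are of interest, an uncontrolled trial cannot identify them reliably, which is itself a reason to show both. This should be corrected in the next amendment. It does not by itself invalidate the design.

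**What to change.** In Appendix 3, reconcile the exacerbation entry, the disease-under-study exemption and the opening sentence of Definition of an SAE. State that the exemption does not apply to an event that meets a seriousness criterion, and remove the hospitalization and death examples from that sentence.

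At minimum, if the exemption is kept, record every death and every unplanned hospitalization for pyoderma gangrenosum with a causality assessment. Tabulate them on the SAF by dosing group, whatever their AE classification, in the interim and final safety outputs. Showing them on separate lines lets a reader see the count with and without them.

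The cost is appendix wording and one table. The downside is a few more SAE reports, some background disease events in the safety count, and a slightly less favourable SAE rate. No treatment rule changes.

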#### An SAE is defined as any untoward medical occurrence that, at any dose:

- Results in death
- Is life-threatening

Life-threatening in the definition of "serious" refers to an event in which the subject was at risk of death at the time of the event. It does not refer to an event which hypothetically might have caused death, if it were more severe.

• Required inpatient hospitalization or prolongation of existing hospitalization

In general, hospitalization signifies that the subject has been detained (usually involving at least an overnight stay) at the hospital or emergency ward for observation and/or treatment that would not have been appropriate in the physician's office or outpatient setting. Complications that occur during hospitalization are adverse events. If a complication prolongs hospitalization or fulfills any other serious criteria, the event is serious. When in doubt as to whether "hospitalization" occurred or was necessary, the adverse event should be considered serious.

Hospitalization for elective treatment of a pre-existing condition that did not worsen from baseline is not considered an adverse event.

• Results in persistent disability or incapacity

The term disability means a substantial disruption of a person's ability to conduct normal life functions. This definition is not intended to include experiences of relatively minor medical significance such as uncomplicated headache, nausea, vomiting, diarrhea, influenza, and accidental trauma (e.g., sprained ankle) which may interfere with or prevent everyday life functions but do not constitute a substantial disruption.

- Is a congenital anomaly or birth defect
- Other situations:
  - Medical or scientific judgment should be exercised in deciding whether SAE reporting is appropriate in other situations such as important medical events that may not be immediately life-threatening or result in death or hospitalization but may jeopardize the subject or may require medical or surgical intervention to

InflaRx Clinical Study Protocol, Version 4.0 Including Amendment 02, 14 May 2020 IFX-1 IFX-1-P2.7

> prevent one of the other outcomes listed in the above definition. These events should usually be considered serious. Examples of such events include invasive or malignant cancers, intensive treatment in an emergency room or at home for allergic bronchospasm, blood dyscrasias or convulsions that do not result in hospitalization, or development of drug dependency or drug abuse.

#### Recording of an Adverse Event and/or SAE

#### Adverse Event and SAE Recording

- When an adverse event/SAE occurs, it is the responsibility of the investigator to review all documentation (e.g., hospital progress notes, laboratory reports, and diagnostics reports) related to the event.
- The investigator will then record all relevant adverse event/SAE information in the CRF.
- It is **not** acceptable for the investigator to send photocopies of the subject's medical records in lieu of completion of the adverse event/SAE CRF page.
- There may be instances when copies of medical records for certain cases are requested by, for example, the IRB or regulatory agency. In this case, all subject identifiers, with the exception of the subject number, will be redacted on the copies of the medical records before submission.
- The will attempt to establish a diagnosis of the event based on signs, symptoms, and/or other clinical information. Whenever possible, the diagnosis (not the individual signs/symptoms) will be documented as the adverse event/SAE.

#### Assessment of Intensity

The investigator will make an assessment of intensity for each adverse event and SAE reported during the study and assign it to 1 of the following categories:

- Mild: an event that is easily tolerated by the subject, causing minimal discomfort and not interfering with everyday activities.
- Moderate: an event that causes sufficiently discomfort and interferes with normal everyday activities.
- Severe: an event that prevents normal everyday activities. An adverse event that is assessed as severe should not be confused with a SAE. Severe is a category utilized for rating the intensity of an event; and both adverse event and SAEs can be assessed as severe.
- An event is defined as 'serious' when it meets at least 1 of the predefined outcomes as described in the definition of an SAE, NOT when it is rated as severe.

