# **Objectives and Endpoints:**

Objectives	Endpoints
Primary	
• Explore the safety of IFX-1 for the treatment of subjects with pyoderma gangrenosum	• Occurrence, nature and intensity of treatment emergent adverse events (TEAEs), related TEAEs, serious TEAEs, and adverse events of special interest
Key Secondary	
• Explore the efficacy of IFX-1 for the treatment of pyoderma gangrenosum	
 
Responder rate defined as Physician's Global Assessment ≤3 of target ulcer at Visits V4, V6, V10, and V16 (End of Treatment [EOT])
 
Time to complete closure of pyoderma
 

	gangrenosum target ulcer (investigator assessment)
• Explore additional clinical outcome parameters in subjects with pyoderma gangrenosum under the treatment with IFX-1	• Percentage change in wound area and wound volume (wound healing) of target ulcer between Visits V1-V4, V1-V6, V6-V10; V10-V16, and V1-V16 (photographic assessment)
	• Rate of change per day in area of target ulcer (photographic assessment)
	• Number of subjects with a decrease in area of target ulcer of 50% or more at Visit V16 (EOT) compared to baseline (photographic assessment)
	• Number of subjects with a decrease in area of target ulcer of 100% at Visit V16 (EOT) compared to baseline (remission) (photographic assessment)
	• Degree of erythema and border elevation of the target ulcer compared to baseline at Visits V4, V6, V10, and V16 (EOT) (investigator assessment)
	• Mean change from baseline in pain assessed by Numeric Rating Scale (NRS) at Visits V4, V6, V10, and V16 (EOT)
	• Mean change from baseline in Dermatology Life Quality Index (DLQI) at Visits V4, V6, V10, and V16 (EOT)

InflaRx	Clinical Study Protocol,
	Version 4.0 Including Amendment 02, 14 May 2020
IFX-1	IFX-1-P2.7

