# 8.2 Discontinuation of the IMP

Subjects must be discontinued from treatment with the IMP because of:

- Unacceptable toxicity or TEAE, as determined by the investigator
- Anaphylactic or other serious allergic reaction
- Serious infection, including meningitis and sepsis
- If, in the investigator's opinion, continued administration of IMP could be detrimental to the subject's well-being
- Use of prohibited treatment that in the opinion of the investigator or sponsor or sponsor's designee necessitates the subject being removed
- Biopsy confirmation of any malignancy
- Pregnancy
- Abnormal liver function meeting Hy's Law criteria (62).

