## 10.3.1 Safety Analyses

The primary objective of this study is to explore the safety of IFX-1 administered in subjects with pyoderma gangrenosum. Safety will be described by the following endpoints:

- TEAEs, defined as adverse events that start at or after the first administration of IMP
- Related TEAEs
- Serious TEAEs
- Adverse events of special interest

TEAEs will be analyzed according to the number and percentage of subjects who had an adverse event as well as the number of TEAEs with the respective MedDRA System Organ Class and Preferred Term. Related TEAEs and serious TEAEs will be analyzed in the same way. Additionally, the number and percentage of subjects with adverse events will be further grouped by severity and relationship. The maximum severity/relationship per subject and preferred term will be counted in these summary tables.

All safety analyses will be performed on the SAF. Analyses will generally be performed for the entire SAF as well as the 3 dosing groups separately. Additional stratifications based on actual dosing and IMP compliance will be defined in the statistical analysis plan.

InflaRx	Clinical Study Protocol,
	Version 4.0 Including Amendment 02, 14 May 2020
IFX-1	IFX-1-P2.7

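### Intensity is graded only by discomfort and daily function, so a symptom-free laboratory, ECG or vital-sign adverse event fits only the mild category, whatever its size.

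*Combined protocol and SAP*

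**What the plan says.** The Synopsis (Objectives and Endpoints) names intensity in the primary endpoint: "Occurrence, nature and intensity of treatment emergent adverse events (TEAEs".

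Appendix 3, under Events Meeting the Adverse Event Definition, brings measured findings into the adverse event definition when the investigator judges them clinically significant: "Any abnormal laboratory test results (hematology, clinical chemistry, or urinalysis) or other safety assessments (e.g., ECG, radiological scans, vital signs measurements".

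Appendix 3, Assessment of Intensity, asks the investigator for an "assessment of intensity for each adverse event and SAE reported during the study and assign it to 1 of the following categories". There are three grades:

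- The lowest grade is worded as "Mild: an event that is easily tolerated by the subject, causing minimal discomfort and not interfering with everyday activities".
- The middle grade joins two conditions, one on how the subject feels and one on how daily life is disturbed.
- The highest grade rests on function alone: "Severe: an event that prevents normal everyday activities".

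The same section keeps seriousness apart from intensity, so SAE status does not raise the grade.

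Section 10.3.1 groups subjects with adverse events by severity and relationship, for the whole safety set and for each dosing group: "The maximum severity/relationship per subject and preferred term will be counted in these summary tables".

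Section 8.2 lists a laboratory-based reason for mandatory discontinuation. The entry opens with "Abnormal liver function meeting" and refers to Hy's Law.

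**The concern.** A scale built on discomfort and function suits events that the subject feels. It gives no way to rank events found only by measurement, yet the protocol requires these to be graded on it as well. A small and a very large symptom-free abnormality receive the same lowest grade, so for such events the grade says nothing about size.

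This matters because intensity is a named component of the primary endpoint and is tabulated by dosing group in a study that compares three dose levels. Sections 3.2.1 and 9.4 show that measured events are relevant to this product. Laboratory, ECG and vital-sign data are all collected as safety variables. Events previously reported as at least possibly related to IFX-1 include increased C-reactive protein, hepatocellular injury, leukocytosis, and changes in blood pressure and heart rate.

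**Working it through.** The plan gives no figure to reproduce on this point. The check applies the definitions to one case, looks for a rule elsewhere that would change the result, and then works out what one subject weighs in the tables.

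**Step 1. Apply the scale.** Take a clinically significant laboratory, ECG or vital-sign finding in a subject without symptoms.

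| Grade | What the definition needs | Met without symptoms? |
|---|---|---|
| Severe | Everyday activities prevented | No |
| Moderate | Discomfort, and interference with activities | No, on both |
| Mild | Easily tolerated, minimal discomfort, no interference | Yes |

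Only mild fits. The size of the abnormality appears in none of the definitions, so it cannot change the result. The same holds for a symptom-free liver abnormality that meets the stopping criterion in Section 8.2.

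**Step 2. Look for a rule that repairs this.**

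- Section 9.4.1 has each abnormal laboratory value marked as clinically significant, not clinically significant, or an error. This is a flag, not a severity grade.
- The clinical-significance judgment in Appendix 3 decides whether a finding becomes an adverse event. It does not grade it.
- Seriousness is a separate axis by the wording of Assessment of Intensity itself.
- Section 10.3.5 summarises laboratory values and changes from baseline by visit, including minimum and maximum. An extreme value would show there, but nothing links it to the grade of the adverse event.

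No legible part of the protocol grades such events by size.

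**Step 3. Weight of one subject.** Section 7.1.2 gives 6 subjects per dosing group and three groups, so 18 in all.

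- One dosing group: 1/6 = 16.7 percentage points
- All subjects: 1/18 = 5.6 percentage points

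The shift applies to the row for that preferred term. It would not occur if the same subject also had a higher-graded event under the same term. These are simply what any one subject contributes to a table of this size; they do not measure how often the problem arises.

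**The case against.** The strongest case on the other side is that a functional intensity scale is a legitimate choice for a small, descriptive study, and that the plan nowhere promises grading by size. The size of abnormalities is reported in the laboratory summaries of Section 10.3.5, and clinically significant values are repeated under Section 9.4.1. No test, threshold or stopping rule uses the intensity grade. Under Section 9.4.9 the move to the next dose group is the sponsor's decision on safety data, with no severity criterion stated.

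Most of this stands, and it limits the reach of the point. It does not remove it: the grade is part of the primary endpoint, and following the rule as written gives an uninformative grade to a whole class of events.

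Four stronger readings are tempting, and the documents do not support them.

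- *A Hy's Law case would be hidden.* It would be a TEAE and a documented discontinuation. It would probably also be an SAE, through the important-medical-event route in Appendix 3.
- *The number of misgraded events can be put at up to 90.* Safety laboratory samples after the first dose fall at V4, V6, V10, V16 and Ob2, and 5 × 18 = 90. That is a ceiling on scheduled sampling occasions if all 18 subjects attend every visit, whereas Section 10.1 expects at least 15 to reach 3 months of treatment. It counts samples, not adverse events, and only findings judged clinically significant are graded at all.
- *The related events seen in earlier studies would have been graded mild here.* Section 3.2.1 does not say that any of them was symptom-free. Several came from patients with sepsis or undergoing cardiac surgery, and the 12-subject hidradenitis study reported no related events.
- *Dose escalation will be misled.* Severity tables may inform the sponsor's judgment, but the documents do not say that the decision rests on them.

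**Conclusion.** The point holds for clinically significant findings without symptoms. On the wording of Appendix 3 these fit only the mild grade, whatever their size, and no legible section corrects this. The defect lies in the intensity component of the primary endpoint and in the maximum-severity tables, not in the detection or reporting of the events. How many events are affected cannot be estimated from the documents. Where one is, the row concerned moves by 16.7 points in a group of 6 and 5.6 points in 18.

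The conclusion rests on three assumptions:

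- Severity in Section 10.3.1 means the intensity grade of Appendix 3.
- Investigators apply the definitions as written. If some grade by medical importance instead, they depart from the definitions, and grades may differ between sites.
- No grading rule stands in the separate SAP announced in Section 10.3 or in the Appendix 1 laboratory table. The first was not available and the second is not legible in the text reviewed, so neither could be checked.

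An event that also causes symptoms or limits activities can be graded higher and falls outside the point.

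**What to change.** In Appendix 3, Assessment of Intensity:

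1. Keep the functional scale for symptomatic events.
2. State that an adverse event consisting of a laboratory, ECG or vital-sign finding is graded by its size, using a published or prespecified grading table fixed before the first interim analysis.
3. If symptoms are also present, use the higher of the two grades in the maximum-severity tables.
4. Apply the same table to events already recorded, from the values on file, so that all dosing groups are graded alike.

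The cost is one table covering the parameters collected, some re-grading, and some less favourable severity grades. No extra visits or samples are needed, and no dose or stopping rule changes. If the SAP or Appendix 1 already holds such a rule, a cross-reference from Appendix 3 would suffice.
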